9.5 Outcomes: Milestone Measures and Data Analyses

Measure 1: Average sleep (REM+nonREM) duration difference between MBI and controls using EEG. Normal preterm brain development is dependent on cycling between wakefulness and sleep with sleep durations gradually increasing by about 5% increments every two weeks until term age. EEG will be used to measure the average duration of sleep (REM + non-REM) between MBI and controls. Average sleep duration measurements will determine if MBI promotes/enhances brain maturation.

Statistical Analysis: Four quality sleep durations from within each EEG session will be averaged per-infant per-timepoint (one EEG session for each of the 4 age timepoints, 30 weeks, 32 weeks, 34 weeks, 36 weeks). At each timepoint, average sleep duration will be compared between MBI infants and controls. Milestone threshold will be reached if >5% longer average durations of sleep are found in the MBI cohort compared to controls in any 1 or more of the serial EEGs.

Measure 2: Late Slow Wave amplitude difference in auditory ERPs comparing MBI to controls. Due to immature nervous systems, early infant neurodevelopment studies have centered on attentional capture paradigms using ERPs. ERPs quantify changes in electrical brain potentials time-locked to a stimulus and are widely used to study cognitive abilities such as learning, discrimination, attention, and memory. At one month age, the ERP Late Slow Wave of a mom/stranger stimulus is considered a reflection of perceptual learning and memory. ERP Late Slow amplitude measurements will determine if MBI enhances neurodevelopment.

Statistical Analysis: ERP Late Slow Wave amplitudes from the 100 trials of the auditory recognition task will be averaged. Within-infant average Late Slow Wave amplitudes across mother's voice trials minus the same average across stranger's voice trials will be computed and averaged. Mother-vs-stranger Late Slow Wave average difference between MBI and controls will be compared. Milestone threshold will be reached if $\ge 1 \ \mu V$ greater amplitude difference in ERPs of the MBI cohort compared to controls is found at one month adjusted age.

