Measure 3: PIPP scores comparing MBI to controls during a painful procedure. The premature infant pain profile (PIPP) is well established and has undergone extensive psychometric testing. Music creates a sense of familiarity and security in preterm infants and redirects their attention away from the painful stimulus; thus, PIPP scores will be used to measure if MBI has an effect on pain response in comparison to controls.

Statistical Analysis: The PIPP will be scored at 3 age timepoints (30 weeks, 32 weeks, 34 weeks). At each timepoint, average PIPP among MBI infants will be compared to average PIPP among control infants. Milestone threshold will be reached if MBI cohort PIPP scores are \geq 1 point lower than controls at any 1 or more of the scoring points.

Measure 4: Central EEG amplitude changes comparing MBI to controls during a painful procedure. The heel lance painful procedure has been shown to evoke central EEG activity with significantly higher amplitudes, $\ge 10 \ \mu\text{V}$ in infants. EEG will be used to measure amplitude changes in central EEG activity to determine if MBI alters responses to a painful procedure.

Statistical Analysis: Three quantifiable changes in central EEG amplitudes will be collected - one for each age timepoint at which a heel lance is done (at 30, 32, and 34 weeks). Within-infant central EEG amplitude differences between heel sticks and resting states will be computed. Average central EEG amplitude change (heel-stick minus resting-state) among MBI infants will be compared to controls. Milestone threshold is reached if $\geq 10 \ \mu V$ attenuation in central EEG amplitudes occurs with a painful procedure in the MBI cohort compared to controls in any of the serial EEGs.

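### Measures 1, 3 and 4 can be met at the 30-week Baseline/Visit 1 alone: this cannot show maturation (Measure 1), and shows a pain effect (Measures 3 and 4) only if music is already playing

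*Combined protocol and SAP*

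**What the plan says.** All three rules are in section 9.5, and each compares a difference between arm averages with a fixed threshold.

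- **Measure 1 (sleep duration).** The plan takes "one EEG session for each of the 4 age timepoints, 30 weeks, 32 weeks, 34 weeks, 36 weeks". The milestone is met if average sleep is more than 5% longer, "found in the MBI cohort compared to controls in any 1 or more of the serial EEGs". The stated purpose is to determine whether MBI enhances brain maturation, and the same paragraph describes normal development as "sleep durations gradually increasing by about 5% increments every two weeks until term age".
- **Measure 3 (PIPP).** "The PIPP will be scored at 3 age timepoints (30 weeks, 32 weeks, 34 weeks"). The milestone is met if the MBI mean is at least "1 point lower than controls at any 1 or more of the scoring points".
- **Measure 4 (central EEG amplitude).** Changes are collected, "one for each age timepoint at which a heel lance is done (at 30, 32, and 34 weeks"). The milestone is met on an attenuation of at least 10 µV "compared to controls in any of the serial EEGs".

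The 30-week timepoint is Visit 1. The section 6 schedule runs from Baseline/Visit 1 to visits at 2, 4 and 6 weeks, section 6.2.2 lists EEG and PIPP among the baseline assessments, and section 9.6 describes the week-4 PIPP as coming after four weeks of MBI. Nothing in section 9.5 sets Visit 1 apart.

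**The concern.** At Visit 1 no weeks of music have accumulated, so the meaning of a between-arm difference there depends on whether music is playing during the recording.

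For Measure 1, the 5% threshold equals one normal two-week increment in sleep, and no two-week interval under music has elapsed. If the EEG precedes music, a difference is chance imbalance. If music is playing, it may be immediate lengthening of sleep, which sections 2.2 and 3 lead one to expect. Neither is maturation.

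For Measures 3 and 4, a recording before the first session cannot show any effect of music on pain. A recording during a session could.

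Section 9.6 compares these quantities with the declared thresholds as Go/NoGo outcomes. A milestone could therefore be credited to Visit 1 while every later visit fails it, including the week-4 PIPP that section 9.2 names as the primary outcome.

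**Working it through.** **Inputs.** From section 9.2: PIPP SD 3.6, 25 per group, alpha 0.05 (taken as two-sided). From section 9.5: threshold 1 point, three visits. Assumed: the same SD and 25 per group at every visit, normal visit differences, and an equal correlation rho between visits. The documents give no rho, so it is varied from 0 to 0.7, with 0.9 as a further check.

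**The plan's own figure.** A two-sample t-test with these inputs has 79.7% power at a difference of 2.9 and 84.7% at 3.1. The stated 80% and 85% reproduce.

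**One visit, no effect.** SE = 3.6 × √(2/25) = 1.018. The threshold is 1/1.018 = 0.982 SE, and P(Z ≥ 0.982) = 16.3%.

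**Any of k visits.** P(met) = 1 − P(every counted visit difference is below 1 point), from the multivariate normal. At rho = 0 with no effect this is 1 − 0.837³ = 41.4% for three visits and 1 − 0.837² = 29.9% for two.

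No effect at any visit:

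| rho | 30, 32, 34 weeks | 32, 34 weeks | added by Visit 1 |
|---|---|---|---|
| 0 | 41.4% | 29.9% | 11.4 points |
| 0.3 | 36.5% | 27.9% | 8.7 |
| 0.5 | 32.9% | 26.1% | 6.8 |
| 0.7 | 28.8% | 23.9% | 4.9 |
| 0.9 | 23.2% | 20.7% | 2.5 |

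With 30 per group at every visit and rho 0.7 to 0, the rates are 25-37% with Visit 1 and 21-26% without.

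Other scenarios, rho 0.7 to 0:

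| True PIPP effect | With Visit 1 | Without |
|---|---|---|
| *Visit 1 precedes music* | | |
| 1-point benefit at weeks 2 and 4 | 63-79% | 63-75% |
| 1 point worse at weeks 2 and 4 | 17-20% | 4-5% |
| *Music plays at Visit 1* | | |
| 1-point benefit at all three visits | 69-88% | 63-75% |
| 1-point benefit at Visit 1 only | 53-65% | 24-30% |
| 1 point worse at all three visits | 5-7% | 4-5% |

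If Visit 1 precedes music, excluding it costs 0-4 points of success for the 1-point benefit and removes 13-16 points when MBI is worse. If music plays, excluding it costs 6-12 points of detection for a constant 1-point benefit, slightly more than the 5-11 points of no-effect rate that it removes.

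**Measures 1 and 4.** The documents give no SD for either, so no rate can be computed.

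**Timing of Visit 1.** Section 6.2.2 places randomization immediately after screening, so allocation is known to the delivery staff before Visit 1. The Figure 4 caption in section 3 describes the biweekly recordings as including MBI or control sessions, with and without pain, and makes no exception for the first. The revision history for Version 7.0 removed the 48-hour period for Visit 1 activities, and the schedule gives Visit 1 no window. The caption suggests that music may be playing; nothing confirms it.

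**The case against.** The strongest case for leaving the rule alone has four parts.

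1. **The any-visit rule is deliberate.** The revision history defends it for sleep, PIPP and EEG amplitude as a search for critical periods in which music may have more impact, and 30 weeks is a listed age. This stands as a defence of the rule at visits with music. It does not address a visit recorded before any music.

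2. **Immediate effects are in scope.** Section 2.1a covers short-term as well as durable pain effects. Section 9.5 explains PIPP partly by music that "redirects their attention away from the painful stimulus", which is an acute mechanism. This stands for Measures 3 and 4. A reader might infer that they are milestones for cumulative effect, so that Visit 1 should be barred whatever its timing. Section 9.5 contains no such restriction, and if music is playing, exclusion costs slightly more detection than the error it removes. For Measure 1 an immediate sleep effect is also plausible, so timing does change what a Visit 1 difference means, but under neither timing is it maturation.

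3. **Visit 1 is a minor contributor.** This stands. The threshold is about one SE and already gives 16% at a single visit; Visit 1 adds 5-11 points, or 2-3 at correlation 0.9. The study is exploratory and these are screening thresholds, not tests.

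4. **The missing material may settle the timing.** Figure 4 itself, the study diagram and Appendix A are not in the available text. This stands, and is why the request on timing is for a statement and not a claim of error. Also, Measures 1 and 3 are compared visit by visit, so a Visit-1-only result could be identified. It would still count as meeting the milestone.

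**Conclusion.** The point holds in a limited form. As section 9.5 is written, Visit 1 alone can satisfy Measures 1, 3 and 4. For Measure 1 that is inconsistent with the measure's stated purpose under either timing. For Measures 3 and 4 it is a defect only if Visit 1 is recorded before the first session.

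For PIPP, Visit 1 raises the no-effect milestone rate by about 5-11 percentage points. This rests on SD 3.6, 25 per arm at each visit and an assumed between-visit correlation of 0.7 to 0.

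A reader might infer more: that Visit 1 is simply a pre-treatment visit, or that Visit 1 makes a false Go likely. The documents support neither. The Figure 4 caption suggests music may be playing at Visit 1, and how the milestones combine into a Go decision is not in the available text, so the effect on that decision cannot be assessed. Confidence is high for Measure 1 and moderate for Measures 3 and 4. The change is worth making because it is cheap and these are Go/NoGo criteria.

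**What to change.** In section 9.5:

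1. Count only the 32-, 34- and 36-week EEGs toward the Measure 1 milestone. Report the 30-week EEG separately, as baseline or as an immediate sleep effect according to timing.
2. State whether the Visit 1 recordings precede the first MBI or control session. If they do, count only 32 and 34 weeks toward Measures 3 and 4.
3. If music plays at Visit 1, leave the any-visit rule for Measures 3 and 4 as it is, report which visit met the threshold, and label a Visit-1-only result as an immediate effect.

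Keep the any-visit rule for the later visits in all cases. If Appendix A or Figure 4 already gives the Visit 1 sequence, repeat it in section 9.5.

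**Cost.** Some wording and one sentence on timing, with no change to visits or sample size. The milestones become slightly harder to reach: for PIPP, 0-4 points of success for a 1-point benefit at weeks 2 and 4 if Visit 1 precedes music, and nothing if music plays there. A sleep effect seen only at Visit 1 would no longer meet Measure 1; it would be reported separately.

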MBI subjects will receive a total of 1.5 hours of music intervention averaged at 4-5 sessions per week (Figure 2). Music will be alternating: 30 minutes on and 30 minutes off and will be played when the subject is awake to cue pacification and initiate the sleep process. Voice unaccompanied or with single accompanying softly arpeggiated instrument⁶⁶ is best for infants. Lullabies meet these criteria and promote language development due to an emphasis on vowels, rising and falling melodic phrases, and the recognition of soothing sounds. Lullabies will all have consistent tempos, with the melody in higher range sung by female or children as infants hear these pitches best.66 As it is recommended to change song order to increase stimulation, habituation, and neurological development, we will use ten playlists. MP3 players will be loaded in advance with the entire 6 weeks

of music. Within each week, order of the playlists will be randomly assigned and prepared in advance by [name]. MBI will have minimal interference with routine medical care. Study coordinators will monitor for any distress from music: finger splay, grimace, vital sign disturbance, or persistent crying.⁶⁷ If crying lasts longer than 5 minutes, the intervention will be stopped for that day's session. Blinding will be maintained by using identical headphones and MP3 players for all subjects. Headphones will be placed on each side of infant's head such that sound stimuli are received binaurally.⁶⁶ Music amplitude will be no more than 70 dB on Scale C.^{15,66,68}

Daily electronic volume level checks will avoid the need for listening checks of the headphones. Headphones will be placed 1 cm away from the ears to avoid discomfort from headphone compression. The headphones will either play music or silence for the control group.

Figure 4: Every two weeks, 30 hour EEG* recordings will capture two sessions of background frequencies and changes that occur with Session 1) MBI or Control intervention or Session 2) [MBI + pain] or [Control + pain]

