6.2.2 Enrollment, Baseline, and/or Randomization

Enrollment

All infants for whom a parent or legal guardian has signed consent will be considered to be enrolled in the study.

Baseline Assessments/ Visit 1

For participants who have successfully been screened for eligibility and are enrolled into the study, baseline assessments are performed. These include the following:

- Demographics
- Medical History
- Physical Exam
- Vital Signs
- Baseline Lab Values
- Concomitant Meds
- HADS (Hospital Anxiety and Depression Scale) for Moms
 - *optional element (mom must provide specific consent to complete this assessment)
- Music Exposure during Pregnancy

- EEG
- PIPP
- Adverse Events
- SAE

Randomization

Once eligibility has been confirmed and consent obtained, subjects will be randomly assigned to the MBI or control treatment cohorts in a 50:50 allocation ratio using randomization tables, stratified by sex, prepared by [name]. Randomization will occur immediately after screening.

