6.2.3 Blinding

Blinding will be maintained by using identical headphones and MP3 players for all subjects. The PI, any personnel involved in collecting the clinical outcomes (e.g., PIPP) or collecting or quantifying EEG outcomes, and the statistician will be blinded. The statistician will be aware of blinded treatment group, so that e.g. safety summaries by blinded treatment group can be prepared for the Data Safety and Monitoring Board (DSMB) closed sessions if it so requests. Should the DSMB request unblinded comparisons, the study team will contract with the University of Minnesota CTSI's Biostatistical Design and Analysis Center (BDAC) for an independent statistician to work with the DSMB using unblinded data.

The unblinded staff includes [name] (music therapist) and [name] (Director of the NICU). [name] will prepare the music players. Both will be unblinded to handle randomization, delivery of interventions, and preparations of unblinded reports to the independent study monitors. They will not be involved with data monitoring, analyses, or outcome assessments.

The study coordinators who are assessing the PIPP will wear earplugs and noise cancelling headphones, which will ensure that s/he cannot hear what is emanating from the infant's headphones. In addition, family members and NICU staff will be reminded frequently to not disclose what they think they hear coming from the infant's headphones.

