9.2 Sample Size and Randomization

The R61 phase is exploratory. Based on the number of eligible infants and assuming 60% of eligible subjects enrollment, we can feasibly enroll 60 infants in 1.5 years.. This sample size is similar to or larger than other MBI studies in infants.^{21,23,68,107}

The clinical measure Premature Infant Pain Profile (PIPP) at 4 weeks is the primary outcome for the R61-phase pilot clinical trial. With expected recruitment of at least 60 preterms, expected 50 completed PIPPs at 4 weeks represents a loss to follow-up of $(60-50)/60 = \sim 17\%$. Such a loss rate is slightly more conservative than previous studies completed in the University of Minnesota NICU (which has had ~15% loss rates). This sample size is similar to or larger than other previous MBI studies in infants.

With 50 completed PIPPs at 4 weeks, for comparing MBI to control (25 per group), there is 80% power to detect a group difference in PIPP of 2.9 and 85% power to detect a group difference in PIPP of 3.1. These calculations assume a between-infant standard deviation of 3.6, estimated from the placebo group of a recent study of sucrose as an analgesic for pain from a standard-of-care heel lance. These calculations were carried out in SAS with the following code:

proc power;

twosamplemeans test=diff meandiff = . stddev = **3.6** npergroup = **25**

```
power = 0.80 0.85
    alpha = 0.05
run;
```

;

The R61 exploratory phase data from primary outcome clinical measure PIPP at 4 weeks will be utilized to assist in planning of the R33 phase. The associations of baseline characteristics (infant, e.g. birthweight, and maternal pregnancy history, etc) may inform the design of the R33 phase. For example, these secondary analyses might indicate that we should stratify randomization in the R33 phase by a dichotomized infant birthweight. These analyses, using linear models or non-parametric alternatives if needed (e.g., measures are highly skewed), will use both intervention groups and we will examine the magnitudes of associations in each group and, if appropriate, in the pooled groups.

Treatment Assignment Procedures

Once eligibility has been confirmed and consent obtained. Randomization will be accomplished through the use of randomization tables, stratified by sex and within each stratum use randomly allocated block sizes of 2 and 4. These will be prepared by the study statistician ([name]).

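### The PIPP milestone can be met by an observed difference of about one standard error at a visit labelled baseline: settle what Visit 1 measures, and show intervals beside the threshold

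*Combined protocol and SAP*

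**What the plan says.** Section 9.2 names one visit: "The clinical measure Premature Infant Pain Profile (PIPP) at 4 weeks is the primary outcome for the R61-phase pilot clinical trial". With 25 per group and an SD of 3.6, "there is 80% power to detect a group difference in PIPP of 2.9", and 85% power for 3.1, from a two-sample comparison at alpha 0.05.

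Section 9.5, Measure 3, states a different rule for the milestone. "The PIPP will be scored at 3 age timepoints (30 weeks, 32 weeks, 34 weeks"), the arms are compared at each, and the milestone is reached if the MBI mean is at least "1 point lower than controls at any 1 or more of the scoring points". No test, interval or error rate is attached. Section 9.6 adds that the Go/NoGo quantities are computed without imputation and set against the thresholds.

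The 30-week score is the first of the three. The schedule of evaluations marks PIPP in the Baseline/Visit 1 column, and section 6.2.2 lists it where "baseline assessments are performed. These include the following". Section 9.6 describes the 4-week score as coming after 4 weeks of MBI, which would put Visit 1 at about zero weeks.

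Other text points the other way. In section 6.2.2, "Randomization will occur immediately after screening", so allocation is known before Visit 1. The Figure 4 caption in section 3 describes two-weekly recordings that include "MBI + pain] or [Control + pain" sessions, and EEG is scheduled at Visit 1. In section 6.2.3, "The study coordinators who are assessing the PIPP will wear earplugs and noise cancelling headphones", with no exception for Visit 1. Section 2.1a seeks immediate as well as lasting effects.

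**The concern.** If no music is given before or during the Visit 1 PIPP, the arms can differ there only by chance. The rule as written would still count a 1-point imbalance at that visit as the milestone reached. The Revision History (Version 2.0b) explains why any visit may count, but not why a visit labelled baseline should.

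Separately, the threshold is small relative to the sampling error of a difference between two arms of 25, and 9.5 does not ask for that error to be shown. At stake is how a met milestone is read when R33 is planned: as a screening signal that chance produces fairly often, or as something firmer.

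**Working it through.** **Inputs.** From section 9.2: SD 3.6, 25 per arm, alpha 0.05 (two-sided reproduces the stated figures). From 9.5: threshold 1 point, three visits. Not in the documents, so assumed: the same SD and number per arm at the other two visits, and an equal between-visit correlation r, shown from 0 to 0.9.

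**1. The plan's own figures.** SE of a difference = 3.6 × √(2/25) = 1.018, with 48 degrees of freedom. The noncentral t gives detectable differences of 2.91 (80% power) and 3.11 (85%). Power is 79.7% at 2.9 and 84.7% at 3.1. Section 9.2 reproduces.

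**2. The threshold on that scale.** 1/1.018 = 0.98 standard errors. The 95% half-width is 2.011 × 1.018 = 2.05 points. An observed 1.0-point benefit therefore has an interval of about -3.05 to +1.05 (p = 0.33).

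**3. One visit, no effect.** P(difference ≤ -1) = 1 - Φ(0.982) = 16.3%.

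**4. Any of k visits, no effect.** P = 1 - ∫ Φ((0.982 - √r·z)/√(1-r))^k φ(z) dz. At r = 0 this is 1 - 0.837³ = 41.4% for three visits and 1 - 0.837² = 29.9% for two.

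| r | 30, 32, 34 weeks | 32, 34 weeks | Visit 1 alone adds |
|---|---|---|---|
| 0 | 41.4% | 29.9% | 11.4 points |
| 0.3 | 36.5% | 27.9% | 8.7 |
| 0.5 | 33.0% | 26.1% | 6.8 |
| 0.7 | 28.8% | 23.9% | 4.9 |
| 0.9 | 23.2% | 20.7% | 2.5 |

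The last column is taken before rounding. Simulation of three visits gives 41.4% at r = 0 and 28.6% at r = 0.7.

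**5. Sensitivity, r from 0.7 to 0, three visits then two.**
- SD 3.0: 22-32%, then 18-22%.
- SD 4.2: 34-49%, then 29-36%.
- 30 per arm at each visit: 25-37%, then 21-26%.

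**6. What leaving out Visit 1 would cost.** Chance of meeting the milestone, r from 0.7 to 0, three visits then two:
- 2-point benefit at 32 and 34 weeks, none at Visit 1: 91-98%, then 91-97%.
- 1-point benefit at 32 and 34 weeks, none at Visit 1: 63-79%, then 63-75%.
- 2-point benefit at Visit 1 only: 84-89%, then 24-30%.

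The first two cases show little loss if Visit 1 carries no effect. The third shows a large loss if it measures an immediate effect.

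**The case against.** The strongest reply is that the plan does what it sets out to do. Section 9.2 ties its power to completed 4-week scores, prints the code, and claims nothing for the milestone. The Revision History says the any-visit rule was chosen on purpose, to find periods of prematurity when music may matter more. It also calls the R61 exploratory and concedes inadequate power for hypotheses 1 and 2. A lenient screen in a pilot is a choice of tolerance. All of this stands. A reader might infer that the power statement is wrong, or that the any-visit rule is an oversight; the documents support neither.

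A second reply is that the Visit 1 score may well be an on-music measurement. Randomization comes first, the painful-procedure sessions are described by arm, Measure 3 treats 30 weeks like the other visits, and assessors are masked by sound at every PIPP. The Revision History (Version 7.0) also records that the 48-hour period for baseline activities was removed, so nothing fixes the score before the first session. This stands too. A reader might infer that the 30-week score must be dropped; the text is too unsettled for that, and step 6 shows the cost if the inference is wrong. What remains is that the label, the visit list and the 9.6 wording point towards a true baseline, and the plan does not resolve the conflict.

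Third, the range rests on assumptions. The 41% end needs zero correlation between scores on the same infant. The range shifts with the assumptions but does not become negligible: even at correlation 0.9 it is 23% with three visits.

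**Conclusion.** The point holds in limited form. As written, the PIPP milestone can be met by a difference of about one standard error at a visit labelled baseline, with no interval beside it. Under SD 3.6, 25 per arm at every visit and correlation 0.7 to 0, it is met with no effect in about 29-41% of trials with three visits and 24-30% with two. At correlation 0.9 the rates are 23% and 21%; over SD 3.0 to 4.2 they span about 22-49% and 18-36%. Visit 1 accounts for 5-11 percentage points at SD 3.6, and those are pure chance imbalance only if no music precedes or accompanies that score.

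A reader might take 29-41% as the chance of wrongly advancing to R33. The documents do not support that. There are four milestones, the Revision History gives them equal weight, and the supplied text does not say how they combine. Section 9.1 refers to Appendix A for the milestones; it is not in the supplied text and may say more.

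The arithmetic is firm; the reading of Visit 1 is open. Severity is minor to moderate.

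**What to change.** In this order:

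1. Reconcile section 3 (Figure 4 caption), the schedule of evaluations, section 6.2.2 and section 9.5 on whether any music is given before or during the Visit 1 PIPP. If none is, count only the 32- and 34-week visits towards the milestone and report Visit 1 descriptively. If it is an on-music measure, say so and keep the three-visit rule.
2. In 9.5, show each visit's difference with its 95% confidence interval beside the 1-point threshold, and identify the 4-week result as the declared primary, so that a met milestone is not read as evidence at the 5% level.
3. Optionally, state the milestone's chance of being met with no effect, using the sponsor's own assumptions for correlation, SD and numbers at each visit.

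The cost is one clarification and some wording in 9.5, with no new data. The any-visit rule stays. The rule should not be changed before item 1 is settled.
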